5.7.2. Immunogenicity (Antibodies to Guselkumab)

Blood samples will be collected to examine the formation of antibodies to guselkumab at the specified visits as shown in the schedule of events of the protocol. Serum samples will also be collected at the final visit from participants who terminate study participation early.

5.7.2.1. Immunogenicity Analysis

The antibodies to guselkumab will be summarized based on Immunogenicity Analysis Set (Section 4). Participants will be analyzed according to the treatment groups that they actually received. No imputation for missing concentration data will be performed.

The following analysis of antibodies to guselkumab will be performed by treatment group:

- Summary of antibodies to guselkumab status
- Summary of neutralizing antibodies to guselkumab status
- List of participants positive for antibodies to guselkumab

In addition, to explore the relationship between antibodies to guselkumab status and serum guselkumab concentrations, efficacy and safety, the following analysis may be performed as appropriate:

- Summary of clinical response (e.g., IGA 0/1 response) by antibody to guselkumab status
- Summary of injection-site reactions by antibody to guselkumab status
- Summary of serum guselkumab concentrations by antibody to guselkumab status
- Plots of median trough serum guselkumab concentrations over time by antibody to guselkumab status

Immunogenicity analyses presentation

Immunogenicity analyses will be summarized through the following time periods:

- Through Week 16
- Through Week 48

For the immunogenicity analyses, the description of treatment groups is as follows:

1. **Placebo** → **Guselkumab** [REDACTED] [REDACTED] Participants randomized to placebo and were switched over to Guselkumab [REDACTED] [REDACTED] (due to CO) at Week 16.
2. **Guselkumab** [REDACTED] at Week 0, Week 4, and then [REDACTED] Participants randomized to guselkumab [REDACTED] at Week 0, Week 4, and then [REDACTED] and received guselkumab [REDACTED] [REDACTED] throughout with an additional dose at Week 4.

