Hepatitis B and C serology l	X															
HIV Ab test	X															
Hematology	X	X	X		X	X		X		X				X	X	X
Chemistry	X	X	X		X	X		X		X				X	X	X
Lipid panel n		X						X						X	X	X
Hs-CRP		X	X			X		X		X				X	X	X
HbA1c		X						X						X	X	X

Phase	Screening a	Placebo b				Active Treatment b								Follow-Up b,c		
Week		0	4	8	12	16	20	24	28	32	36	40	44 (last dose)	48 (Final Efficacy)	Early Term.	56 (Final Safety)
Clinical Pharmacology and Biomarker Assessments p																
Serum guselkumab concentration		X	X			X				X				X	X	X
Anti-guselkumab antibodies		X	X			X				X				X	X	X
Serum biomarkers		X	X			X				X				X		
Optional Substudies e																
Skin biopsy p		X				X								X		
Tape stripping		X	X			X				X				X		
Whole blood (pharmacogenomics) q		X														
Ongoing Participant Review																
Concomitant therapy	X	X	X	X	X	X	X	X	X	X	X	X	X	X	X	X
Adverse events	X	X	X	X	X	X	X	X	X	X	X	X	X	X	X	X

a: The screening visit should occur within approximately 4 weeks before the Week 0 visit.

b: All post-baseline visits will have a visit window of  $\pm 7$  days counting from Week 0 as Day 1.

c: If a participant permanently discontinues study drug intervention prior to the Week 16 visit, they should be encouraged to return for all remaining study visits through Week 16, and the participant should also return for a final visit to perform assessments under the Week 56/final safety visit approximately 12 weeks after the last study intervention administration. If a participant permanently discontinues study drug at or after the Week 16 visit, they should complete the Week 48/final efficacy visit assessments at the time of discontinuation, or as soon as possible, and also return for a final safety visit to perform assessments under the Week 56/final safety visit approximately 12 weeks after the last study intervention administration.

d: All study procedures and evaluations should be completed before administration of study drug.

e: ICFs must be signed before the first study-related activity. The optional skin biopsy, tape stripping, and pharmacogenomics substudies will use separate ICFs.

f: Details may be found in the Photography Manual.

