###### **Immunogenicity Analyses**

The incidence and titers of antibodies to guselkumab will be summarized for all participants who receive at least 1 dose of guselkumab and have appropriate samples for detection of antibodies to guselkumab (i.e., participants with at least 1 sample obtained after their first dose of guselkumab).

A listing of participants who are positive for antibodies to guselkumab will be provided.

The incidence of NAb to guselkumab will be summarized for participants who are positive for antibodies to guselkumab and have samples evaluable for NAb to guselkumab. Other immunogenicity analyses may be performed to further characterize the immune responses that are generated.

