1.2. Study Design

This is a Phase 3b, multicenter, randomized, double-blind, placebo-controlled study designed to evaluate the efficacy and safety of guselkumab versus placebo in participants with low BSA moderate plaque psoriasis with special site involvement.

Approximately 300 eligible participants will be randomized in a 2:1 ratio to receive either guselkumab [REDACTED] at Weeks 0 and 4 and then [REDACTED] or placebo (Figure 1). Randomization will be stratified by qualifying special sites (i.e., scalp, face, intertriginous, and genital) with approximately 25% of participants per each special site. If participants present with qualifying moderate psoriasis in multiple special sites, they will be allocated to the special site that is most severe, as determined by the participant. The study will aim to enroll no less than approximately 20% of participants from diverse racial-ethnic backgrounds (i.e., self-identify as non-white/non-Caucasian descent) to reflect the North American Census population.

There will be 2 treatment groups:

- A guselkumab group who will receive guselkumab [REDACTED] [REDACTED] at Weeks 0 and 4 and then [REDACTED] through Week 44. Placebo will be administered at Week 16 to maintain the blind.
- A placebo group who will receive placebo at Weeks 0, 4, and 12 after which they will cross over to receive guselkumab at Weeks 16, 20, 28, 36, and 44.

Further details on active and blinding study intervention administrations for both treatment groups are provided in Section 6.

There will be 2 database locks (DBLs) in this study, at Weeks 16 and 56. After all participants have completed the Week 16 visit (or discontinued from the study), a Week 16 DBL will be performed, and unblinded data will only be made available to select Sponsor and Contract Research Organization (CRO) team members involved with analysis of the data and preparation of analyses for the Week 16 DBL. All other Sponsor, site, and CRO personnel directly involved

with study conduct will remain blinded to treatment assignments until the Week 56 DBL and related analyses have been completed. A diagram of the study design is provided in [Figure 1](#).

[figure not shown]
Week 0 through Week 16 (Placebo Controlled Period)

- Group I (n=200): guselkumab CCI CC at Weeks 0, 4, and 12. Placebo will be administered at Week 16 to maintain the blind.
- Group II (n=100): placebo at Weeks 0, 4, and 12 followed by guselkumab CCI at Weeks 16

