5. STATISTICAL ANALYSES

5.1. General Considerations

In general, descriptive statistics will include counts and percentages for categorical variables, and mean, standard deviation (SD), median, interquartile (IQ) range, minimum, and maximum for continuous variables. Graphical data displays may also be used to summarize the data.

In this study, efficacy will be evaluated through Week 48. In addition, PK, immunogenicity, PD, biomarker, and safety measurement, and selected participant information data will be collected through Week 56.

Analyses and summaries (including overtime summaries) in general will be carried out during the following study periods when appropriate:

1. From Week 0 through Week 16 (Placebo Controlled Period)
2. From Week 0 through Week 48 (Placebo Controlled and Active Treatment Period)
3. From Week 0 through Week 56

Binary Response Efficacy Endpoints

For binary response efficacy endpoints, treatment comparisons will generally be performed using a Cochran-Mantel-Haenszel (CMH) test stratified by special site (scalp, face, intertriginous, and genital) involvement. The magnitude of the treatment difference will be estimated by the difference in response rates between the guselkumab and placebo groups with a 95% confidence interval (CI) calculated based on Wald statistics (Kim and Won, 2013).

For special site related binary response efficacy endpoints, treatment comparisons will generally be performed using a Chi-squared test. The magnitude of the treatment difference will be estimated by the difference in response rates between the guselkumab and placebo groups with a 95% confidence interval (CI) calculated.

In case of rare events the Fisher's exact test will be used for treatment comparisons as appropriate. The proportion difference between guselkumab group and placebo and the exact confidence interval will be calculated. In these analyses, participants with missing data will be imputed as not achieving the response.

Continuous Efficacy Endpoints

For continuous efficacy endpoints, treatment comparisons will be performed using a Mixed Effects Model for Repeated Measures (MMRM), which relies on the Missing at Random (MAR) assumption for the missing responses. Under the assumption of MAR, the missing data will be accounted for through correlation of repeated measures in the model.

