Population PK analyses will be performed to characterize the disposition characteristics of guselkumab based on the guselkumab concentration data from PSO studies. Data may be combined with other selected studies to support a relevant structural model. A detailed analysis plan for population PK analysis will be developed separately, and a stand-alone technical report will be written to summarize the results of the population PK analysis.

PK analyses presentation

PK analyses will be summarized through the following time periods:

- Through Week 16
- Through Week 48

For the analyses, a Participant is included in one and only one treatment group on the basis of the treatment regimen followed. The description of treatment groups are as follows:

1. **Placebo → Guselkumab** ███ ███ Participants randomized to placebo and were switched over to Guselkumab ███ ███ (due to CO) at Week 16.

2. **Guselkumab** [REDACTED] at Week 0, Week 4, and then [REDACTED] Participants randomized to guselkumab [REDACTED] at Week 0, Week 4, and then [REDACTED] and received guselkumab [REDACTED] [REDACTED] throughout.

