5.7.2.2. Other Immunogenicity Analyses

No other immunogenicity analysis is planned.

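### SAP 5.7.1 and 5.7.2.1 end the PK and immunogenicity summaries at Week 48 although Week 56 samples are scheduled, so cumulative antibody incidence may be understated

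*SAP*

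**What the plan says.** Sampling: in protocol 1.3 (Schedule of Activities), the row "Anti-guselkumab antibodies" is marked at Weeks 0, 4, 16, 32, 48, Early Termination and 56. The serum concentration row is identical. The last dose is at Week 44. The final safety visit is about 12 weeks after the last dose, including for participants who stop treatment early. SAP 5.1 agrees: "PK, immunogenicity, PD, biomarker, and safety measurement, and selected participant information data will be collected through Week 56". It also lists Week 0 through Week 56 among its analysis periods, with the qualification that the periods apply in general and when appropriate.

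Summaries: SAP 5.7.1 states "PK analyses will be summarized through the following time periods" and SAP 5.7.2.1 states "Immunogenicity analyses will be summarized through the following time periods". Each then names Week 16 and Week 48 and nothing later. SAP 5.7.2.2 adds "No other immunogenicity analysis is planned".

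Protocol analysis: section 9.4.6.1 says "The incidence and titers of antibodies to guselkumab will be summarized for all participants who receive at least 1 dose of guselkumab", given at least one sample after the first dose. It sets no last week. The Immunogenicity Analysis Set in SAP Section 4 sets none either. The safety summaries in SAP 5.6 do run through Week 56.

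**The concern.** The section-specific lists are the ones a programmer would follow. Under them the final scheduled antibody sample is taken but does not enter the incidence, titer or neutralizing-antibody summaries. Antibody status is cumulative: a participant is positive if any post-dose sample is positive. Someone who first turns positive at Week 56 would then be reported as negative.

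The omitted sample also differs in kind from the rest. It is the one taken after drug has had about 12 weeks to decline, while the earlier samples are taken much closer to a dose. Evaluating PK and immunogenicity is a stated objective, although it is listed among the other objectives and is descriptive.

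**Working it through.** **Inputs**
- Sampling weeks (protocol 1.3): 0, 4, 16, 32, 48, 56.
- Crossover-arm guselkumab doses (SAP 1.2): this arm will "cross over to receive guselkumab at Weeks 16, 20, 28, 36, and 44".
- Guselkumab-arm doses (SAP 1.2): Weeks 0, 4 and 12 are printed and the later interval is redacted. Weeks 20, 28, 36 and 44 are an inference: dosing runs through Week 44, and the only blinding placebo listed for this arm is at Week 16.
- Samples are drawn before dosing at dosing visits (protocol 1.3 footnotes).

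**The plan's own figure.** Last dose to final safety visit: 56 − 44 = 12 weeks, which agrees with the stated interval of about 12 weeks.

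**Time since the preceding guselkumab dose** (sample week − last earlier dose week)

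| Sample | Guselkumab arm | Crossover arm |
|---|---|---|
| Week 4 | 4 − 0 = 4 | no guselkumab yet |
| Week 16 | 16 − 12 = 4 | no guselkumab yet (pre-dose) |
| Week 32 | 32 − 28 = 4 (inferred dose) | 32 − 28 = 4 |
| Week 48 | 48 − 44 = 4 | 48 − 44 = 4 |
| Week 56 | 56 − 44 = 12 | 56 − 44 = 12 |

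**Scheduled post-dose antibody samples summarized**
- Guselkumab arm: 4 through Week 48 and 5 through Week 56, so the cut drops 1 of 5.
- Crossover arm: 2 through Week 48 and 3 through Week 56, so the cut drops 1 of 3.

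**Early stoppers.** With a last dose at Week 36, the final safety visit is at about 36 + 12 = Week 48. With an earlier last dose it comes sooner. Their 12-week sample can therefore fall inside the Week 48 window.

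**Direction.** In a fixed analysis set, the number ever positive through Week 48 is at most the number ever positive through Week 56. The two are equal if nobody first turns positive at Week 56. The same holds for the number with neutralizing antibodies. Protocol 9.4.6.1 summarizes neutralizing antibodies among antibody-positive participants, so that percentage could move either way as its denominator grows.

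**Size.** No antibody rate is given. As an assumption only, suppose 300 participants are sampled at Week 56 and a share p is first positive then. The number missed is 300 × p: 0 at p = 0%, 1.5 at 0.5%, 3 at 1%, 6 at 2% and 15 at 5%.

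**Trough label.** SAP 5.7.2.1 offers one optional display, "Plots of median trough serum guselkumab concentrations over time by antibody to guselkumab" status. No sample is scheduled at Weeks 12, 20, 28, 36 or 44. Week 4 in the guselkumab arm is a pre-dose sample on active drug. The Week 16 (guselkumab arm), 32 and 48 samples are 4 weeks after a dose and, on the inferred schedule, not immediately before the next one.

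**The case against.** The strongest reply is that the Week 56 data are not clearly excluded. SAP 5.1 lists a Week 56 analysis period, the Immunogenicity Analysis Set has no week limit, SAP 5.7.1 promises concentrations at each visit, the listing of positive participants has no period of its own, and population PK goes to a separate plan with no stated cut-off. This stands to the extent that the SAP contradicts itself, so exclusion is not certain. It does not remove the point. The 5.1 list is qualified, the specific sections name shorter periods, and 5.7.2.2 plans nothing further. A listing and a population PK model do not replace an incidence table.

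Two further objections stand and limit the fix. Efficacy ends at Week 48, so Week 48 is a defensible cut for response by antibody status. SAP 5.7.1 also removes by-visit concentrations once a participant discontinues guselkumab or has another dosing deviation, so early stoppers' final-visit concentrations cannot simply be added.

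A reader might infer more than the documents support in three places:
- That incidence *is* understated. This needs at least one first positive at Week 56, and no rate is given.
- That Week 56 provides the only samples 12 weeks after a last dose. This holds for scheduled samples in participants who complete dosing, not for early stoppers.
- That mid-interval concentrations are generally presented as troughs. The word is used for one optional plot; the main PK summaries refer to concentrations.

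**Conclusion.** The point holds as an inconsistency with a one-directional consequence. The PK and immunogenicity sections stop at Week 48, against a sampling schedule that runs to Week 56 and against SAP 5.1, the Immunogenicity Analysis Set and protocol 9.4.6.1, none of which imposes that limit. Followed literally, the specific sections omit 1 of 5 scheduled post-dose antibody samples in the guselkumab arm and 1 of 3 in the crossover arm. For completers, the omitted sample is the only scheduled one about 12 weeks after a dose.

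The numbers of antibody-positive and neutralizing-antibody-positive participants may be too low and cannot be too high. The shortfall may be zero and cannot be computed from the documents. Concentration summaries are not cumulative, so for PK the loss is one visit's data rather than a bias in incidence.

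The conclusion about periods needs no assumption. The statement about time since dose in the guselkumab arm at Week 32, and the trough remark for that arm's maintenance period, rest on the inferred dosing weeks. The primary and major secondary efficacy analyses are not affected.

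**What to change.** 1. In SAP 5.7.2.1, add a period through Week 56 (keeping Weeks 16 and 48) for the antibody-status, titer and neutralizing-antibody summaries. Count all samples after the first guselkumab dose, including final-safety-visit samples from participants who stop early.
2. In SAP 5.7.1, add the Week 56 visit to the by-visit concentration summaries and leave the dosing-deviation exclusions as they are.
3. Keep Week 48 for efficacy by antibody status, and say that status there is determined through Week 48.
4. Alternatively, if Week 48 is intended throughout, state why and reconcile it with SAP 5.1 and protocol 9.4.6.1.
5. Minor: in the optional trough plot, label values by nominal time since last dose.

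The cost is SAP wording and a little extra table work. No new samples are needed, and alpha and power are unaffected. Reported antibody incidence may be slightly higher.

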5.7.2.2. Other Immunogenicity Analyses

No other immunogenicity analysis is planned.

5.7.3. Pharmacodynamics

Samples for serum biomarkers will be collected for all participants as indicated in the Schedule of Activities in the protocol. The analyses on PD biomarkers are to better understand the biology of PSO, to provide a biological assessment of the participants' response to treatment with guselkumab, to analyze differences between responders and non-responders, and to determine if the markers can be used to classify participants as potential responders prior to treatment.

All PD analyses will be based on the PD Analysis Set (Section 4). Participants will be analyzed according to the treatment groups that they received. No imputation for missing concentration data will be performed. Detailed analysis plan and the PD analyses results will be provided in an independent technical report.

5.7.4. Pharmacokinetic/Pharmacodynamic Relationships

If data permit, the relationships between serum guselkumab concentration and efficacy may be analyzed graphically. If any visual trend is observed, a suitable population PK/PD model may be developed to describe the exposure-response relationship. Details will be given in a population PK/PD analysis plan and results of the population PK/PD analysis will be presented in a separate technical report.

5.7.5. Biomarkers Analyses

Biomarker analysis may be deferred or not performed, if during or at the end of the study, it becomes clear that the analysis will not have sufficient scientific value for biomarker evaluation, or if there are not enough samples or responders to allow for adequate biomarker evaluation. In the event the study is terminated early or shows poor clinical efficacy, completion of biomarker assessments is based on justification and intended utility of the data.

DNA samples may be analyzed if it is hypothesized that this may help resolve issues with the clinical data. DNA samples will be used for research related to guselkumab or psoriasis. They may also be used to develop tests/assays related to guselkumab and psoriasis. Pharmacogenomic research may consist of the analysis of one or more candidate genes or of the analysis of genetic markers throughout the genome (as appropriate) in relation to guselkumab or psoriasis clinical endpoints. Results will be presented in a separate report.

5.7.6. Health Economics

No health economics measurement is collected in this study.

5.7.7. Other Variables and/or Parameters**5.7.7.1. Definition****5.7.7.2. Analysis Method****5.7.8. Definition of Subgroups**

To evaluate the consistency of efficacy based on demographic characteristics, baseline disease characteristics, and psoriasis medication history, subgroup analyses will be performed for the primary endpoint and selected major secondary endpoints. The subgroups for subgroup analyses include, but are not limited to, the following:

Baseline demographics

- Sex (male, female)
- Race/ethnicity (White, Black, Asian, Hispanic or Latino, Multi-Racial, Middle Eastern, American Indian/Indigenous/Alaskan Native, Pacific Islander/Native Hawaiian, Other)
- Geographic location ((United States, Canada)
- Baseline Age (≤ 30 , >30 to ≤ 45 , >45)
- Baseline weight (≤ 90 kg, >90 kg)
- Baseline weight by quartiles
- BMI (Normal [<25], Overweight [25 to <30], Obese [≥ 30])

Baseline disease characteristics:

- Age at diagnosis (years) (<25 , ≥ 25)
- Psoriasis disease duration (years) (≤ 2 , >2 to ≤ 5 , >5)
- Psoriatic arthritis (3 groups: Yes Rheumatologist confirmed; PEST positive at screening, PEST negative at screening)
- Special site as randomized (Scalp, Face, Intertriginous, Genital)
- Additional special site (, Palmoplantar, Nail)
- Baseline DLQI (<10 , ≥ 10)
- Baseline PASI (<10 , ≥ 10 to <15 , ≥ 15)
- Baseline BSA (≥ 2 to <5 , ≥ 5 to <10 , ≥ 10 to ≤ 15)

Psoriasis medication history:

- Phototherapy (ultraviolet B light [UVB] or psoralen and ultraviolet A light therapy [PUVA])
 - ☐ Never used
 - ☐ Ever used
- Conventional systemics (PUVA, MTX, cyclosporine, acitretin)

-
- ☐ Never used
 - ☐ Ever Used
 - Advanced Orals (apremilast, deucravacitinib,)
 - ☐ Never used
 - ☐ Ever used
 - Topicals
 - ☐ Never used
 - ☐ Ever used
 - Participants who had an inadequate response to or intolerance to any of the following phototherapy: Ultraviolet B light [UVB] or psoralen and ultraviolet A light therapy [PUVA]
 - Yes
 - No
 - Participants who had an inadequate response to, or intolerance to any of the conventional systemic therapies (PUVA, MTX, acitretin or cyclosporine)
 - Yes
 - No
 - Participants who had an inadequate response to or intolerance to any of the conventional systemics, phototherapy, or apremilast
 - Yes
 - No
 - Participants who had an inadequate response to or intolerance to any of the advanced oral systemic therapies (apremilast, deucravacitinib,)
 - Yes
 - No

